Our target number of subjects to include in the fMRI analyses is N=30 (15 confirmed HS+ and 15 confirmed HS-). Because we have not yet identified a mechanism by which we can predict hormone sensitive status at baseline with 100% accuracy, we will need to over-recruit women with a history of PND to account for those who end up not being HS+. In our previous study 11 of the 15 women (73%) with a history of PND were HS+. For the current study, we therefore plan to over-enroll women with a history of PND in order to reach our target of 15 women with confirmed HS+. If 73% of women with a history of PND and no history of non-puerperal major depressive disorder are HS+, then we will need to enroll 21 women to find 15 with confirmed HS+. Based on the 9% dropout rate of our prior trial, we estimated a 9% dropout rate, and as such, we have budgeted for an additional 3 subjects to account for dropouts. In the prior study 2/3 of the women who withdrew from the protocol had a history of PND, so we anticipate 2 women with a history of PND and 1 control (without a history of PND) will withdraw from the proposed study. These numbers are summarized in the following table:

Recruitment Group	Target Enrollment	Confirmed HS+/HS- (included in fMRI/behavioral analysis)	Not HS+/HS- (excluded from fMRI/behavioral analysis)	Withdrawn
History of PND	23	15 HS+	6 not HS+	2
Control (no history of PND)	16	15 HS-	0 not HS-	1
TOTAL	39	30	6	3

Thus, we plan to enroll a total of 39 subjects (n=16 without a history of PND, n=23 with a history of PND).

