Dependent variable: Threat attention bias will be measured using the visual dot probe task at study visits 3 and 6. Threat attention bias will be calculated for the angry-neutral trials by subtracting the mean reaction time (measured in milliseconds) on trials where the asterisk

appears on the same side as the angry face from the mean reaction time on trials where the asterisk appears on the same side as the neutral face.

Analysis: 2x2 Repeated Measures ANOVA will be used to analyze the effects of Group (HS- vs. HS+) and Phase (baseline vs. hormone addback) on threat attention bias.

Power: We used G*Power 3.1 for Mac to calculate power. We anticipate an effect size $f=0.3$ based on a previous study of threat attention bias in those with and without mood dysregulation (Hommer et al., 2014). If we set $\alpha=.05$, we will have 87% power to reject the null hypothesis with a total sample size of $N=30$.

Null hypothesis 1b: HS+ is not characterized by reduced amygdala-medial PFC connectivity in response to threatening stimuli during hormone addback relative to baseline in the target population.

Alternative hypothesis 1b: HS+ is characterized by reduced amygdala-medial PFC connectivity in response to threatening stimuli during hormone addback relative to baseline in the target population.

Independent variables: Group (HS+ versus HS-) and Phase (Visit 3-baseline versus Visit 6-hormone addback)

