Dependent variable: Amygdala-medial PFC connectivity will be assessed during the implicit face emotion processing fMRI task at study visits 3 and 6. Functional connectivity expresses the statistical dependency among activations in different brain regions and results in undirected (symmetrical) connectivity matrices and will be calculated according to standard procedures (Walsh et al., 2017). We will use a generalized psychophysiological interaction (gPPI) approach for detecting context-dependent functional connectivity (Cisler et al., 2014; McLaren et al., 2012). Replicating the methods of Walsh et al. (2017), we will use an ROI approach to target the amygdala, which will be defined using the Harvard-Oxford subcortical atlas. Voxel-wise models will be used to evaluate connectivity with the amygdala seed. For each participant, mean fMRI time courses will be extracted from the amygdala seed using the “fslmeans” program in FSL, then multiplied by each psychological regressor of interest (i.e., task condition) to form the PPI interaction terms. The gPPI model will include physiological and psychological regressors, as well as their interaction terms to describe the unique effect of these interactions above and beyond the main effects of seed time courses and task conditions. Our primary contrast of interest will evaluate the difference between connectivity during presentation of threatening stimuli versus non-threatening stimuli. This allows for the characterization of connectivity patterns specific to threat processing.

Analysis: Group and phase differences will be evaluated with respect to seed-based connectivity specific to threat processing using a 2x2 mixed effects analysis with Bayesian estimation techniques with FMRIB Local Analysis of Mixed Effects (Smith et al., 2004).

Clusters will be thresholded at $Z>2.58$ or $p<.005$ corrected with a minimum contiguous cluster size of 8 (Walsh et al., 2017).

Power: We used G*Power 3.1 for Mac to calculate power. While few studies have examined changes in amygdala-PFC between those with and without depression following treatment, the few extant studies yielded large effects ($d=1.3$) (Straub et al., 2017). If we anticipate an effect size $f=.5$ and set $\alpha=.05$, we will have greater than 99% power to reject the null hypothesis with a total sample size of $N=30$.

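### The power printed for Hypothesis 1b belongs to a single-value test at alpha .05, not to the voxel-wise cluster test that the plan will run, whose power the documents do not allow anyone to compute

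*Combined protocol and SAP*

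**What the plan says.** All of the conflicting text stands under Hypothesis 1b in section 7.2 of the combined protocol and SAP.

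- Design: "Independent variables: Group (HS+ versus HS-) and Phase (Visit 3-baseline versus Visit 6-hormone addback").
- Dependent variable: generalized psychophysiological interaction with an amygdala seed. "Voxel-wise models will be used to evaluate connectivity with the amygdala seed".
- Analysis: a 2x2 mixed-effects group model in FLAME. "Clusters will be thresholded at $Z>2.58$ or $p<.005$ corrected with a minimum contiguous cluster size of 8".
- Power: "We used G*Power 3.1 for Mac to calculate power". The basis is that "the few extant studies yielded large effects ($d=1.3"). Then: "If we anticipate an effect size $f=.5$ and set $\alpha=.05$, we will have greater than 99% power to reject the null hypothesis", with a total of 30 women.

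Section 7.1 fixes the split at 15 confirmed HS+ and 15 confirmed HS-. Section 3.2 lists this connectivity measure as one of the two primary endpoints of Aim 1. Section 7.2 also applies Bonferroni to all hypothesis tests and says that non-significant tests will be reported as inconclusive.

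**The concern.** A G*Power calculation with one f, one alpha and one N treats the outcome as a single number per woman per visit. It has no search region, no spatial smoothness and no cluster extent. The 1b Analysis paragraph describes a search over many voxels, in which a finding is a cluster that passes a height cut and an extent rule. The two paragraphs describe different tests.

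No other part of the document supplies a scalar 1b test to which the figure could belong. The fMRI analysis text in section 6 names medial PFC as an a priori region but gives no rule for extracting one connectivity value. The Study Summary and the analysis strategy in Appendix C describe a 2x2 analysis of percent signal change by region, not of connectivity. Hypothesis 1c needs one connectivity value per woman and only refers back to 1b.

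At stake is how a primary result is weighed. A reader who sees a null 1b map beside a stated power above 99% will take the map as near-decisive. That weight has not been earned for the test being run.

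**Working it through.** **Inputs.** From section 7.2 (1b): f=.5, alpha .05, N=30, 2 groups by 2 visits, cited d=1.3, threshold Z>2.58 or p<.005 corrected, extent at least 8. From section 7.1: 15 per group. Not stated: the G*Power module and the correlation between visits. I assume the within-between interaction with correlation rho=.5, and show other values.

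**1. Reproduce the printed figure.** Noncentral F with 1 and 28 df:

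lambda = f² × N × m / (1 − rho) = .25 × 30 × 2 / .5 = 30.

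Power at alpha .05 is 99.96%. With rho=.3 (lambda 21.4) it is 99.4%, and with rho=0 (lambda 15) it is 96.2%. As a check on the choice of module, the same formula at f=.3 gives 88.7% for Hypothesis 1a, against 87% printed. The between-groups main effect at f=.5 and rho=.5 gives 86.3%, which does not match. So the figure above 99% is sound arithmetic for one value measured twice per woman and tested at .05.

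**2. What the planned threshold is.** Z>2.58 corresponds to p=.0049 one-sided or .0099 two-sided, at each voxel, before any correction. The text also says corrected and adds the 8-voxel extent, but names no correction method. Whichever was meant, it is not one F test at .05.

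**3. Power of the planned test.** This needs the number of voxels searched, the smoothness, the spatial extent of the true effect and the correction method. None is given, so no value can be derived.

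**4. Single-value figures, for scale only.** The 2x2 interaction equals a two-sample t test on change, with noncentrality d × √(15/2). Setting d² × 7.5 = lambda = 30 gives d=2.0 on change for f=.5 at rho=.5, which is larger than the cited 1.3.

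| Effect (15 per group) | alpha .05 | .01 two-sided | .005 two-sided |
|---|---|---|---|
| f=.5, rho=.5 (d=2.0 on change) | 99.96% | 99.5% | 98.8% |
| f=.5, rho=.3 | 99.4% | 96.2% | 93.2% |
| f=.5, rho=0 | 96.2% | 85.6% | 78.6% |
| d=1.3, read as group difference in change | 93% | 78% | 69% |

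The first row isolates the stricter alpha: it costs about one percentage point. The last row also changes the effect size, which alone lowers power to 93% at .05.

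**The case against.** The strongest reply is that the mismatch may do little harm. At the plan's own f=.5 and the assumed correlation of .5, a single value tested at two-sided .01 still has 99.5% power, so the printed statement would remain true at that level. This stands, and it rules out saying that the stricter threshold by itself destroys the power.

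A reader might infer that the 1b test must have less power than printed because every reading of the threshold is stricter than .05. The documents do not support that. Z>2.58 is a cut at each voxel, not the rejection level of the hypothesis. If it is applied without correction across a region, any qualifying cluster counts, and both the false-positive rate and the power can exceed those of a single voxel. In simulated null maps under assumed conditions (15 per group, smoothness 2.5 to 3.5 voxels, 1,000 to 2,744 voxels, one-sided Z>2.58, at least 8 contiguous voxels), some cluster appeared in 13% to 44% of maps. These settings are not in the plan. They show only that the direction is open.

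A reader might also take 69% to 78% as the power of 1b, and so expect a true effect to be missed in about a quarter to a third of such trials. Those figures are for one fixed value and rest on reading the cited d=1.3 as a group difference in change, which the plan does not say.

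Nor does the plan let a null map end the research. Section 7.2 already commits to calling it inconclusive. The remark in section 7.1 about whether the work merits pursuit follows the calculation for d=1.10, and the outcomes listed there do not include connectivity.

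None of this makes the printed figure the power of the planned test.

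**Conclusion.** The point holds as a mismatch between the Power and Analysis paragraphs of one primary hypothesis. The figure above 99% is correct arithmetic for a scalar test at .05, given the assumed module and correlation, and it does not describe the voxel-wise cluster test. The power of that test is unknown, and the documents do not establish that it is lower, or by how much. The single-value range at two-sided .005 runs from 98.8% (f=.5, rho=.5) to 69% (d=1.3 on change). It shows how much the stated confidence depends on an effect scale and a correlation that the plan leaves open. The sample size of 30 is not put in doubt by this point. The text should be corrected because 1b is a primary endpoint and the correction is cheap.

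**What to change.** Remove the claim of more than 99% power for the voxel-wise test in the 1b Power paragraph, then choose one of two routes.

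(a) Pre-specify one extracted amygdala-medial PFC gPPI value per visit as the primary 1b test, with the voxel-wise map as supportive. State its power at the alpha actually applied, with the effect size and correlation written out. For example, if the four primary tests (1a, 1b, 2a, 2b) share .05, alpha is .05/4 = .0125, and power is 99.6% at f=.5 and rho=.5, or 81% at d=1.3 on change. This also gives 1c the single value that it needs.

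(b) Keep the voxel-wise test. Name the search region and the correction method, settle whether Z>2.58 is a cluster-forming cut or the final level, and report simulated power with its assumptions, or state that power for the corrected map was not calculated.

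The cost of (a) is a short text change and an extraction rule. The cost of (b) is a fuller threshold definition and, if power is reported, a simulation. In both cases the stated power becomes less favourable or less certain. Enrolment, visits and scans are unaffected.

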7.3 Subject Population(s) for Analysis

The rationale for the proposed study is that employing a scaled down model of puerperal hormonal events permits the identification of a group of individuals homogeneous for hormone sensitivity (HS+),

hence creating the best opportunity for disentangling the specific changes in brain function due to reproductive hormones (i.e., HS-) from those accompanying reproductive hormone-precipitated affective dysfunction (i.e., HS+). Thus, we will only include those with confirmed HS+ and HS- in our planned analyses as described in section 7.2.

8 Safety and Adverse Events

8.1 Definitions

Unanticipated Problems Involving Risk to Subjects or Others

Any incident, experience, or outcome that meets all of the following criteria:

- Unexpected in nature, severity, or frequency (i.e. not described in study-related documents such as the IRB-approved protocol or consent form, the investigators brochure, etc.)
- Related or possibly related to participation in the research (i.e. possibly related means there is a reasonable possibility that the incident experience, or outcome may have been caused by the procedures involved in the research,
- Serious (as defined below) “Serious” is different than “severe” as reported in the CTC criteria that applies a grade to the AE.

Adverse Event

An **adverse event** (AE) is any symptom, sign, illness or experience that develops or worsens in severity during the course of the study. Intercurrent illnesses or injuries should be regarded as adverse events. Abnormal results of diagnostic procedures are considered to be adverse events if the abnormality:

- results in study withdrawal
- is associated with a serious adverse event
- is associated with clinical signs or symptoms
- leads to additional treatment or to further diagnostic tests
- is considered by the investigator to be of clinical significance

Serious Adverse Event

Adverse events are classified as serious or non-serious. A **serious adverse event** is any AE that is:

- fatal
- life-threatening
- requires or prolongs hospital stay
- results in persistent or significant disability or incapacity
- a congenital anomaly or birth defect
- an important medical event

Important medical events are those that may not be immediately life threatening, but are clearly of major clinical significance. They may jeopardize the subject, and may require intervention to prevent one of the other serious outcomes noted above. For example, drug overdose or abuse, a seizure that did not result in in-patient hospitalization, or intensive treatment of bronchospasm in an emergency department would typically be considered serious.

All adverse events that do not meet any of the criteria for serious should be regarded as **non-serious adverse events**.

Adverse Event Reporting Period

The study period during which adverse events will be reported is normally defined as the period from the initiation of any study procedures to the end of the study treatment follow-up. For this study, the study treatment follow-up is defined as 30 days following the last administration of study treatment.

Pre-existing Condition

A pre-existing condition is one that is present at the start of the study. A preexisting condition will be recorded as an adverse event if the frequency, intensity, or the character of the condition worsens during the study period.

General Physical Examination Findings

At screening, any clinically significant abnormality will be recorded as a preexisting condition. At the end of the study, any new clinically significant findings/abnormalities that meet the definition of an adverse event will also be recorded and documented as an adverse event.

Post-study Adverse Event

All unresolved adverse events will be followed by the investigator until the events are resolved, the subject is lost to follow-up, or the adverse event is otherwise explained. At the last scheduled visit, the investigator will instruct each subject to report any subsequent event(s) that the subject, or the subject's personal physician, believes might reasonably be related to participation in this study. The investigator will notify the study sponsor of any death or adverse event occurring at any time after a subject has discontinued or terminated study participation that may reasonably be related to this study. The sponsor will also be notified if the investigator should become aware of the development of cancer or of a congenital anomaly in a subsequently conceived offspring of a subject that has participated in this study.

Abnormal Laboratory Values

A clinical laboratory abnormality should be documented as an adverse event if any one of the following conditions is met:

- The laboratory abnormality is not otherwise refuted by a repeat test to confirm the abnormality
- The abnormality suggests a disease and/or organ toxicity
- The abnormality is of a degree that requires active management; e.g. change of dose, discontinuation of the drug, more frequent follow-up assessments, further diagnostic investigation, etc.

Hospitalization, Prolonged Hospitalization or Surgery

Any adverse event that results in hospitalization or prolonged hospitalization will be documented and reported as a serious adverse event unless specifically instructed otherwise in this protocol. Any condition responsible for surgery will be documented as an adverse event if the condition meets the criteria for an adverse event.

Neither the condition, hospitalization, prolonged hospitalization, nor surgery are reported as an adverse event in the following circumstances:

- Hospitalization or prolonged hospitalization for diagnostic or elective surgical procedures for a preexisting condition. Surgery should **not** be reported as an outcome of an adverse event if the purpose of the surgery was elective or diagnostic and the outcome was uneventful.
- Hospitalization or prolonged hospitalization required to allow efficacy measurement for the study.
- Hospitalization or prolonged hospitalization for therapy of the target disease of the study, unless it is a worsening or increase in frequency of hospital admissions as judged by the clinical investigator.

COVID-19

Any participant that develops symptoms of COVID-19 including by not limited to: fever, cough, shortness of breath, nausea, abdominal pain, headache, loss of taste or smell, or has known contact with a COVID-19 positive carrier will be asked to contact their PCP, their local COVID-19 hotline and the study team immediately. All study procedures will be put on hold until the participant has received a negative test result or has quarantined for 14 days while monitoring their symptoms. If a participant is confirmed positive for COVID-19, the appropriate case report forms will be completed in accordance with CDC guidelines and UNC Policy.

8.2 Recording of Adverse Events

At each contact or virtual visit with the subject, the investigator will seek information on adverse events by specific questioning and, as appropriate, by examination. Information on all adverse events will be recorded immediately in the source document, and also in the appropriate adverse event module of the case report form (CRF). All clearly related signs, symptoms, and abnormal diagnostic procedures results will be recorded in the source document, though will be grouped under one diagnosis.

All adverse events occurring during the study period will be recorded. The clinical course of each event will be followed until resolution, stabilization, or until it has been determined that the study treatment or participation is not the cause. Serious adverse events that are still ongoing at the end of the study period will be followed up to determine the final outcome. Any serious adverse event that occurs after the study period and is considered to be possibly related to the study treatment or study participation will be recorded and reported immediately.

8.3 Reporting of Serious Adverse Events and Unanticipated Problems

Investigators and the protocol sponsor must conform to the adverse event reporting timelines, formats and requirements of the various entities to which they are responsible, but at a minimum those events that must be reported are those that are:

- related to study participation,
- unexpected, and
- serious or involve risks to subjects or others
(see definitions, section 8.1).

If the report is supplied as a narrative, the minimum necessary information to be provided at the time of the initial report includes:

- Study identifier
- Subject number
- A description of the event
- Date of onset
- Current status
- Whether study treatment was discontinued
- The reason why the event is classified as serious
- Investigator assessment of the association between the event and study treatment

8.3.1 Investigator reporting: notifying the study sponsor

Any study-related unanticipated problem posing risk of harm to subjects or others, and any type of serious adverse event, will be reported to the study sponsor and DSMB by telephone within 24 hours of the event. To report such events, an FDA Form 3500A will be completed by the investigator, signed by the sponsor, and faxed to the DSMB within 24 hours. The investigator will keep a copy of this FDA Form 3500A on file at the study site.

Within the following 48 hours, the investigator must provide further information on the serious adverse event or the unanticipated problem in the form of a written narrative. This should include a copy of the completed FDA Form 3500A, and any other diagnostic information that will assist the understanding of the event. Significant new information on ongoing serious adverse events should be provided promptly to the study sponsor and the FDA.

8.3.2 Investigator reporting

For reportable deaths, the initial submission to the UNC IRB may be made by contacting the IRB Director or Associate Director. The AE/Unanticipated Problem Form is required as a follow up to the initial submission.

Other Reportable events:

For clinical drug trials, the following events are also reportable to the UNC IRB:

- Any adverse experience that, even without detailed analysis, represents a serious unexpected adverse event that is rare in the absence of drug exposure (such as agranulocytosis, hepatic necrosis, Stevens-Johnson syndrome).
- Any adverse event that would cause the sponsor to modify the investigators brochure, protocol or informed consent form, or would prompt other action by the IRB to assure protection of human subjects.
- Information that indicates a change to the risks or potential benefits of the research, in terms of severity or frequency. For example:
- An interim analysis indicates that participants have a lower rate of response to treatment than initially expected.

- Safety monitoring indicates that a particular side effect is more severe, or more frequent than initially expected.
- A paper is published from another study that shows that an arm of your research study is of no therapeutic value.
- Change in FDA safety labeling or withdrawal from marketing of a drug, device, or biologic used in a research protocol.
- Breach of confidentiality
- Change to the protocol taken without prior IRB review to eliminate apparent immediate hazard to a research participant.
- Incarceration of a participant when the research was not previously approved under Subpart C and the investigator believes it is in the best interest of the subject to remain on the study.
- Complaint of a participant when the complaint indicates unexpected risks or the complaint cannot be resolved by the research team.
- Protocol violation (meaning an accidental or unintentional deviation from the IRB approved protocol) that in the opinion of the investigator placed one or more participants at increased risk, or affects the rights or welfare of subjects.

